**Table 8: Operating Characteristics for Subject Accrual Suspension Rules**

True Toxicity Rate	Accrual Suspension Probability	Achieved Sample Size		
		25th	50th	75th percentiles
0.1	0.001	80	80	80
0.2	0.018	80	80	80
0.3	0.202	80	80	80
0.4	0.759	14	34	80
0.5	0.991	7	14	25
0.6	1.000	6	8	14

An internal safety review committee consisting of representatives from Clinical Development, Drug Safety, Biostatistics, other functional representatives, as needed, and at least one Principal Investigator will meet at least quarterly to review safety data for potential safety risks or more frequently if needed. If it is determined there is a high probability of observing more than 30% toxicities, enrollment will be suspended and the safety review committee will be convened to make a recommendation on the continuation, modification, or discontinuation of the study.

### 10.3 Replacement of Subjects

Subjects in the dose escalation phase who do not complete Cycle 1 of treatment for reasons other than a DLT will be replaced to provide sufficient number of subjects included for the dose escalation decision. During dose expansion, subjects will not be replaced.

### 10.4 Analysis Sets

Safety Population: All subjects who receive at least one dose (or partial dose) of study treatment will be included in the analysis of safety.

DLT Population: All subjects who complete at least one cycle of treatment or discontinue from the study treatment due to DLT will be included.

Pharmacokinetic Population: All subjects in the Safety Population who have relatively complete individual analyte concentration-time profiles that allow for the computation of meaningful PK parameter values.

Response Evaluable Population: Subjects who have measurable disease (per RECIST 1.1) at baseline and also have one post-baseline assessment of tumor response or are withdrawn due to progressive disease/death prior to first response assessment.

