#### 4.1.2 Open-label Treatment

##### 4.1.2.1 Part 1: Dose Escalation

Subjects will be enrolled in groups of at least 3 subjects in each cohort during the dose escalation phase.

The first dose to be studied will be 0.003 mg/kg administered as an IV infusion over 15 ( $\pm$  5) minutes every 21 days (q21d). Dose escalation will be carried out as listed in [Table 5](#). Dose levels for a given cohort, as listed in [Table 4](#), may be reduced by 25-50% depending on the severity, duration and frequency of toxicities as well as the PK profile, if available, observed at the previous dose level. A subject's dose level may not be escalated once assigned.

For each dose level, the first subject enrolled will be dosed on Cycle 1 Day 1 and monitored for safety and tolerability on Cycle 1, Days 1 through 5, before additional subjects are dosed.

In situations where a cohort of 3 subjects has been enrolled and additional subjects in screening have been deemed eligible for the study, these additional eligible subjects may be enrolled to the cohort. In the event of more than 3 subjects being enrolled to a cohort, the dose escalation decision will be made when the first 3 subjects in the cohort have completed their first cycle (i.e. completion of cycle or occurrence of a dose-limiting toxicity [DLT]). Moreover, the cohort safety review committee or Sponsor may determine that inadequate information has been obtained in a cohort of 3 subjects and to further understand the benefit/risk profile at a given dose level, additional subjects may be enrolled.

Additional subjects may be enrolled at other doses and frequencies deemed to be safe to more fully explore the safety, tolerability, pharmacokinetics, biomarker assessments, and preliminary efficacy of NKTR-214. These additional cohorts of up to 12 subjects may be enrolled to further evaluate NKTR-214 at the recommended phase 2 dose or at doses at or below the MTD.

During dose escalation, subjects who are withdrawn from the study during Cycle 1 for reasons other than occurrence of a DLT will be replaced.

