### Dose Escalation Scheme

For each dose level, the first subject enrolled to the dose cohort will be treated and monitored from Cycle 1, Day 1 through Cycle 1, Day 5 for tolerance prior to the dosing of additional subjects at that dose level. The first subject enrolled to the study will be administered NKTR-214 at the first dose level of 0.003 mg/kg (**Table 4**). Enrollment into the next cohort cannot begin until a full cycle has elapsed since the last subject's first dose in the previous cohort. If no DLTs occur in a cohort of 3 subjects, a new cohort of 3 subjects will be treated at the next higher dose level (**Table 5**). If only 1 of 3 subjects in a cohort experiences a DLT, that cohort will be expanded to 6 subjects. If only 1 of the 6 subjects experiences a DLT, then the next cohort of 3 subjects will be treated at the next higher dose level. If 2 or more subjects within a cohort experience DLTs, then that dose level will be above the MTD (the highest dose tested where no more than 1 of 6 subjects has experienced a DLT), and new subjects will be enrolled at the previous lower (tolerated) dose level until that cohort has 6 subjects. A subject who is withdrawn from the study during Cycle 1 for reasons other than a DLT will be replaced. Approximately 50 subjects will be enrolled into the dose escalation phase of the study.

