3 STUDY DESIGN AND PLAN

This is a Phase 1/2, open-label, multicenter, dose escalation and dose expansion study of NKTR-214 in subjects with histologically confirmed locally advanced or metastatic malignancies who have measurable disease. The study will consist of a dose escalation phase and a dose expansion phase.

The 3+3 design will be used as a guide to determine the MTD in the dose escalation phase. Additional eligible subjects may be enrolled into the cohort for which the first three subjects are under dose-limiting toxicity (DLT) observation. However, the dose escalation decision will be made when the first 3 subjects in the cohort have completed their DLT observation period. During

the dose escalation period, subjects who are withdrawn from the study during the DLT observation period due to reasons other than toxicity will be replaced. All drug related AEs, including events beyond the DLT observation period, will be taken into account to determine the MTD.

Once the MTD has been reached, lower dose and different dose schedules may be assessed.

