7 ANALYSIS POPULATIONS

Safety Population: all subjects who receive at least one dose (or partial dose) of study treatment will be included in the analysis of safety.

DLT Population: all subjects who complete at least one cycle of treatment or discontinue from the study treatment due to DLT will be included.

Pharmacokinetic Population: all subjects in the Safety Population who have relatively complete individual analyte concentration-time profiles that allow for the computation of meaningful PK parameter values.

Response Evaluable Population: subjects who met all eligibility criteria, have measurable disease (per Response Evaluation Criteria in Solid Tumors [RECIST) 1.1) at baseline, and also have at least one post-baseline assessment of tumor response.

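### The DLT Population and the replacement rules turn on why a subject left Cycle 1, while the escalation rule counts a DLT when it occurs; SAP 3 and the protocol also differ on who is replaced

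*Protocol*

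**What the plan says.** Protocol 10.4 defines the DLT Population: "All subjects who complete at least one cycle of treatment or discontinue from the study treatment due to DLT will be included". SAP 7 repeats it: "all subjects who complete at least one cycle of treatment or discontinue from the study treatment due to DLT will be included".

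The protocol's replacement rules also look at why the subject left. Section 10.3: "Subjects in the dose escalation phase who do not complete Cycle 1 of treatment for reasons other than a DLT will be replaced", and the stated purpose is "to provide sufficient number of subjects included for the dose escalation decision". The Dose Escalation Scheme: "A subject who is withdrawn from the study during Cycle 1 for reasons other than a DLT will be replaced". The body of 4.1.2.1: "subjects who are withdrawn from the study during Cycle 1 for reasons other than occurrence of a DLT will be replaced". Section 6.3 replaces early drop-outs unless they stopped because of a DLT.

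The escalation decision is worded differently. Section 4.1.2.1 treats a subject's first cycle as finished when the cycle ends or a DLT occurs. Table 5 counts subjects with a DLT at the dose level. Section 6.9 assesses DLTs in everyone enrolled to the cohort. None of these refers to the DLT Population. Its stated use is the DLT incidence table in protocol 10.5.2, which the synopsis lists among the primary safety analyses.

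SAP 3 describes replacement of subjects who leave the DLT observation period "due to reasons other than toxicity will be replaced". SAP 10 uses the Safety Population for safety analyses by default, and SAP 10.1, on DLTs, names no other set. SAP 14 declares no changes from the protocol's analyses.

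**The concern.** A DLT need not end treatment: protocol 6.10.1 allows dosing to resume after some Grade 3 toxicities, and protocol 5.3 lists exit reasons, such as withdrawn consent, that are separate from toxicity. A subject can therefore have a DLT and still have something else recorded as the reason for leaving Cycle 1. That subject meets neither arm of the DLT Population definition, and the replacement rules read literally call for a substitute.

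Two things are at stake. The reported DLT incidence, a primary safety result based on cohorts of 3 to 6, would omit a real DLT. And section 10.3 links replacement to the escalation decision, so the protocol gives a safety review two standards for the same subject: occurrence of the DLT, or reason for leaving.

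A separate inconsistency is that SAP 3 exempts from replacement anyone leaving because of toxicity, while the protocol exempts only those leaving because of a DLT.

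**Working it through.** The documents give no operating characteristics for the 3+3 rule and no derivation of the approximately 50 escalation subjects, so there is no stated figure to reproduce. The check is first a reading of the rules, then a sensitivity calculation.

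**1. How each rule treats a subject who leaves Cycle 1 early**

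| Subject | DLT Population (protocol 10.4, SAP 7) | Protocol replacement | SAP 3 replacement | 3+3 count (4.1.2.1, Table 5, 6.9) |
|---|---|---|---|---|
| DLT, leaves because of it | In | No | No | DLT counted |
| DLT, leaves for a recorded non-toxicity reason | Out | Yes | Yes | DLT counted |
| Non-DLT toxicity, leaves because of it | Out | Yes | No | No DLT to count |
| No DLT, leaves for a non-toxicity reason | Out | Yes | Yes | No DLT to count |

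Row 2 is the conflict between occurrence and reason for leaving. Row 3 is the conflict between protocol and SAP. They are different subjects.

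**2. Effect of row 2 on the incidence table.** Take three subjects, one with a DLT who then withdraws consent.
- Counted on occurrence: 1/3.
- Protocol DLT Population: 0/2, or 0/3 once a DLT-free replacement completes Cycle 1.
- SAP default (Safety Population): the three treated subjects plus that replacement, 1/4.

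**3. Effect of row 3.** Under SAP 3, one exit for a non-DLT toxicity leaves two evaluable subjects of three (or five of six). Table 5 is written for 3 and 6. Removing a DLT-free subject raises the DLT proportion: one DLT among the remaining two is 1/2, not 1/3.

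**4. Effect on escalation if row 2 subjects really were dropped from the 3+3 count.** A single lost DLT changes the action at each threshold: 1/3 (add three) becomes 0/3 (escalate), and 2/6 (stop) becomes 1/6 (acceptable). On average, let p be the true DLT rate and q the share of DLT subjects lost and replaced. Both are assumptions; the documents give neither.

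- P(escalate past a dose) = (1−p)³ + 3p(1−p)² × (1−p)³
- DLT rate among counted subjects: p′ = p(1−q)/(1−pq)

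At p = 0.40:
- q = 0: 0.6³ + (3 × 0.4 × 0.36) × 0.6³ = 0.216 + 0.432 × 0.216 = **0.309**
- q = 0.05: p′ = 0.38/0.98 = 0.388, giving **0.330**
- q = 0.10: p′ = 0.36/0.96 = 0.375, giving **0.351**
- q = 0.20: p′ = 0.32/0.92 = 0.348, giving **0.401**

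Simulation gave 0.351 and 0.401 for the last two. At p = 0.30 the sequence is 0.494, 0.516, 0.539, 0.588; at p = 0.50 it is 0.172, 0.187, 0.203, 0.242.

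**The case against.** The strongest reply is that the 3+3 decision never uses the DLT Population. Table 5, section 6.9 and the decision timing in 4.1.2.1 all work on occurrence. A reader might infer that a DLT can vanish from the escalation count; the documents do not say so. That reply stands. What remains is a risk, because section 10.3 ties a replacement rule based on reason for leaving to the escalation decision.

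A reader might also infer that the protocol–SAP difference helps hide a DLT, or that every part of this problem errs towards escalation. Neither is supported. The difference concerns only subjects without a DLT, and leaving them out raises the DLT proportion.

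The gap is also narrow. Drug is given once per cycle, so a subject who stops after a DLT may still be observed to the end of Cycle 1. Scans are every 8 weeks, so progression on a scheduled scan would not normally fall within a 14- to 28-day cycle. A drug-related death is Grade 5 and would ordinarily be a DLT itself. Events meeting DLT criteria go to the sponsor within 24 hours, and SAP 10.1 lists every DLT by subject, so the event stays visible. All of this limits how often the case arises; it does not correct the definition.

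Finally, a conditional figure can look alarming. If the exit has happened, the other two subjects are DLT-free and the rate is assumed to be 0.33, the cohort reads 0/3 with probability 1 − 0.33 = 0.67, and escalation follows with probability 0.67 + 0.33 × 0.67³ = 0.77. But a correctly counted 1/3 still escalates with probability 0.67³ = 0.30, and the contrast takes the rare exit as given. It does not measure the size of the problem.

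**Conclusion.** The concern holds in limited form. The DLT Population wording, the same in both documents, gives a wrong result for a subject with a Cycle 1 DLT and another recorded exit reason: that DLT leaves the protocol's incidence table and the reported rate falls. The replacement rules, read literally, replace the same subject, contrary to the occurrence-based 3+3 count.

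The protocol and SAP also disagree on replacing a subject who leaves for a non-DLT toxicity, and SAP 14 does not acknowledge it. The consequence is fewer than 3 or 6 evaluable subjects under the SAP. Because SAP 10.1 names no analysis set, the two documents can also report different DLT rates from the same data.

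The average effect is small if such exits are rare. With an assumed true rate of 0.40 and an assumed 5% or 10% of DLT subjects lost, escalation probability would rise by 0.021 or 0.042 (0.330 − 0.309 and 0.351 − 0.309), and only if the safety review applied the replacement wording over Table 5. Part 2 monitoring is unaffected: Table 7 counts treated subjects, and expansion subjects are not replaced.

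**What to change.** - **Protocol 10.4 and SAP 7:** define the DLT Population as dose escalation subjects who have a DLT in Cycle 1, whatever the reason for discontinuation, or who complete Cycle 1.
- **Protocol 4.1.2.1, 6.3 and 10.3:** state that a subject who has had a Cycle 1 DLT is counted in the escalation decision and is not replaced. This carries the occurrence standard already in 4.1.2.1 and Table 5 into the replacement rules.
- **SAP 3:** reconcile the replacement wording with protocol 10.3, so that both documents treat a subject leaving for a non-DLT toxicity in the same way.
- **SAP 10.1:** name the DLT Population as the set for the DLT summary, in line with protocol 10.5.2.

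The cost is wording in the two documents. No extra subjects, visits or procedures are needed.

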## 10.5 Planned Analyses

### 10.5.1 Demographics and Baseline Characteristics

Demographic data (age, sex, ethnicity, body weight) and baseline disease characteristics will be tabulated and summarized by dose cohort (for the dose escalation phase) and by tumor type (for the dose expansion phase) and presented in data listings.

### 10.5.2 Safety

The primary endpoints of the study are to determine the MTD with NKTR-214. Adverse events and toxicity will be evaluated according to NCI CTCAE version 4.03. Safety assessments will be performed by medical review of AEs and laboratory results.

Incidence rate of DLT will be tabulated by dose cohort for the DLT population.

Treatment emergent AEs (TEAEs) within each system will be summarized by preferred term, system organ class, NCI-CTCAE grade of severity, and relationship to the study treatment. Serious AEs and AEs leading to study drug discontinuation will also be summarized.

A TEAE is defined as an AE that was not present prior to treatment with study treatment, but appeared following treatment or was present at treatment initiation, but worsened during treatment. An AE that was present at treatment initiation, but resolved and then reappeared while the subject was on treatment, is a TEAE (regardless of the intensity of the AE when the treatment was initiated).

Vital signs (including change in weight) and clinical laboratory test results will be summarized descriptively by dose (for the dose escalation phase) and by tumor type (for the dose expansion phase). Any significant physical examination findings will be listed. ECG and echocardiogram data will be evaluated by central review and abnormalities, if present, will be listed. A separate listing and summary of all immune-related AEs (irAEs) will be provided. A listing and summary of subjects who discontinued study drug due to an adverse event will be provided.

A data listing for deaths will be provided.

### 10.5.3 Efficacy

The efficacy outcomes will include:

1. objective response rate (ORR)
2. best overall response (BOR)

■ [REDACTED]

4. duration of response (DOR)

5. clinical benefit rate (CBR)

6. time to response (TTR)

■ [REDACTED]

The primary efficacy measurement will be ORR per RECIST v1.1 based on the Response Evaluable population by tumor type. The number and proportion of subjects with objective tumor response (CR and PR) will be calculated based on number of subjects with measurable disease at baseline. Ninety-five percent (95%) confidence interval (CI) will also be calculated using exact binomial method. Data listing for tumor assessments and tumor response will be provided.

A secondary measurement will be BOR per RECIST v1.1 based on the Response Evaluable population by tumor type. The number and proportion of subjects with a best overall response of CR or PR will be calculated based on number of subjects with measurable disease at baseline. Ninety-five percent (95%) CI will also be calculated using exact binomial method.

DOR will be defined as the time from first documented CR or PR until the earliest evidence of disease progression, new subsequent anti-cancer therapy, or death from any cause. DOR will be estimated using Kaplan-Meier method for those subjects who have a CR or PR.

Clinical benefit rate will be calculated as the number of subjects with confirmed CR, PR, or SD (where the duration of SD should be  $\geq 3$  months) divided by the total number of subjects in the Response Evaluable Population. The number and proportion of subjects with clinical benefit will be summarized.

The time to response will be summarized descriptively for subjects who have a CR or PR.

[REDACTED]

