Statistical Methods:	Safety: The primary safety analyses will include incidence of DLTs by dose cohort. Safety analyses will summarize the incidence, grade and duration of toxicities according to the National Cancer Institute Common Terminology Criteria for AEs (NCI-CTCAE), version 4.03. All AEs will be listed and tabulated by system organ class, preferred term, and coded according to the Medical Dictionary for Regulatory Activities

	
(MedDRA). The incidence of AEs will be tabulated and reviewed for potential significance and clinical importance. Vital signs (including change in weight) and clinical laboratory test results will be listed and summarized descriptively by dose (for the dose escalation phase) and by tumor type (for the dose expansion phase). Any significant physical examination findings will be listed. ECG data will be evaluated by central review. Abnormalities, if present, will be listed. A separate listing and summary of all immune-related AEs (irAEs) will be provided.
 
Efficacy:
 
Efficacy assessments will be summarized separately for the dose escalation and dose expansion cohorts. In order to assess preliminary efficacy, the primary efficacy outcome measurement ORR, and the secondary efficacy outcomes, BOR, CBR, and TTR, will be tabulated by dose and tumor type. [REDACTED]
 
[REDACTED] Individual tumor measurements, tumor size and percent changes in tumor size will be listed. Changes in tumor size will be presented graphically for each specific tumor type. ORR and BOR will each be estimated based on the response evaluable population which is defined as subjects with measurable disease at baseline who receive the study drug and also have one post-baseline assessment of tumor response or are withdrawn due to progressive disease/death prior to first response assessment. DOR will be estimated for subjects who achieve complete response (CR) or partial response (PR). Other secondary efficacy analyses will be based on the all treated population and may be done for the response evaluable population as sensitivity analyses.
 
Pharmacokinetic parameters will be tabulated and summarized with descriptive statistics by dose level. Values for biomarker expression will be calculated at each observation time. Changes in expression from screening to each observation time will be assessed.

--	---

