## 5.0 SELECTION OF STUDY POPULATION

### 5.1 Inclusion Criteria

#### For Parts 1 and 2

1. Willing and able to provide written informed consent.
2. Histologically confirmed diagnosis of a locally advanced (not amenable to curative therapy such as surgical resection) or metastatic solid tumor.
3. Male or female patients, age 18 years or older at the time of signing the informed consent form (ICF)
4. Life expectancy >12 weeks.
5. Patients must not have received interleukin-2 [IL-2] therapy within 12 months of Cycle 1 Day 1.
6. Eastern Cooperative Oncology Group (ECOG) performance status 0 to 1.
7. Measurable disease per RECIST v1.1
8. Sample of archival tumor tissue and fresh baseline tumor biopsies (fresh baseline biopsy is defined as a biopsy specimen taken within 28 days prior to Cycle 1, Day 1) are required, except if inaccessible with Medical Monitor approval. Subjects must consent to allow acquisition of existing formalin-fixed paraffin-embedded (FFPE) material, either a block or unstained slides for performance of correlative studies.
9. Demonstrated adequate organ function, as defined below, within 14 days of treatment initiation:
  - a. WBC count  $\geq 2000/\mu\text{L}$  (after at least 7 days without growth factor support or transfusion)
  - b. Absolute neutrophil count (ANC)  $\geq 1500/\mu\text{L}$  (after at least 7 days without growth factor support or transfusion)
  - c. Platelet count  $\geq 100 \times 10^3/\mu\text{L}$  (transfusions allowed)
  - d. Hemoglobin  $\geq 9.0 \text{ g/dL}$  (transfusions allowed)
  - e. Serum creatinine  $\leq 2 \text{ mg/dL}$  (or glomerular filtration rate  $\geq 40 \text{ mL/min}$ )

- f. Aspartate aminotransferase (AST) and alanine transaminase (ALT)  $\leq 3X$  upper limit of normal (ULN)
  - g. Total bilirubin within normal limits unless associated with hepatobiliary metastases or Gilbert's syndrome, in that case total bilirubin  $\leq 2x$  ULN
10. On stress echocardiogram, documented left ventricular ejection fraction  $>45\%$  on cardiac stress test within 60 days prior to Cycle 1 Day 1. At the discretion of the Investigator, patients who are unable to perform a stress echocardiogram may instead have a multigated acquisition (MUGA) scan or transthoracic echocardiogram (TTE).
11. Oxygen saturation  $\geq 92\%$  on room air. NSCLC patients may use supplemental oxygen.

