9 EFFICACY ANALYSIS

Efficacy analysis will include best overall response (BOR), objective response rate (ORR), clinical benefit rate (CBR), duration of response (DOR), time to response (TTR), [REDACTED]

All tumor response and time to event data will be listed by subject.

9.1 *Best Overall Response*

All lesions, including lymph nodes, will be categorized as target or non-target lesions at baseline and evaluated at each post-baseline tumor assessment to determine the overall response as one of the following: complete response (CR), partial response (PR), stable disease (SD), progressive disease (PD), and not evaluated (NE) based on RECIST 1.1 (E.A. Eisenhauer et al. 2009). The best overall response is determined based on the overall response from each post-baseline tumor assessment in the following order: CR, PR, SD, PD, and NE. For CR and PR, changes in tumor measurements must be confirmed by a repeat assessment at least 4 weeks after the time when criteria for CR or PR are first met. The number and percentage of subjects in each best overall response category will be summarized based on response evaluable population.

9.2 *Objective Response Rate and Clinical Benefit Rate*

ORR is defined as the proportion of subjects who have confirmed CR or PR as their best overall response. CBR is defined as the proportion of subjects who have CR, PR or SD as their best overall response. The number and percentage of subjects who achieve objective response or clinical benefit will be summarized based on response evaluable population. The 95% exact confidence interval using Clopper-Pearson method will be calculated for ORR and CBR. The maximum percentage decrease from baseline in sum of the longest diameter of all target lesions will be plotted for each subject. In addition, BOR and ORR will also be summarized based on all subjects treated.

The immune-related response criteria (irRC) (J.D. Wolchok 2009) may be applied to re-evaluate BOR, ORR, and CBR. The number and percentage of subjects in each category per irRC will be summarized similarly.

All lesion measurements and tumor response assessments will be provided in a listing.

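### Protocol 10.5.3 gives the primary ORR two denominators, which differ by subjects with no post-baseline scan who were not withdrawn for progression or death

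*Protocol*

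**What the plan says.** Two consecutive sentences of protocol 10.5.3 set the base for the primary efficacy measure. The first reads: "The primary efficacy measurement will be ORR per RECIST v1.1 based on the Response Evaluable population by tumor type". The next says that the count and percentage of "subjects with objective tumor response (CR and PR) will be calculated based on number of subjects with measurable disease at baseline". The BOR paragraph in the same section has the same pair of statements. For CBR, by contrast, the section divides explicitly by the total number in the Response Evaluable Population.

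Protocol 10.4 makes Response Evaluable narrower than measurable disease at baseline. Its members must have measurable disease and must "also have one post-baseline assessment of tumor response or are withdrawn due to progressive disease/death prior to first response assessment". Protocol 5.1, criterion 7, makes "Measurable disease per RECIST v1.1" an entry requirement for both parts, so the second denominator is in effect everyone eligible who is enrolled.

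The other places that name a base for ORR choose Response Evaluable. The synopsis states: "ORR and BOR will each be estimated based on the response evaluable population". SAP 9.2 states: "The number and percentage of subjects who achieve objective response or clinical benefit will be summarized based on response evaluable population". SAP 9.2 then adds a summary of BOR and ORR on all treated subjects, without calling it primary, supportive or sensitivity. SAP 14 says that no changes from the protocol analyses are planned.

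**The concern.** ORR is a primary objective, estimated without a comparator in about 50 RCC subjects in Part 2. The denominator therefore acts directly on the estimate and its interval. A subject with no post-baseline assessment cannot be a responder, so removing that subject cannot lower ORR, and raises it whenever there is at least one response. Protocol 10.3 does not replace expansion subjects, so such losses are not made up.

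A programmer working from 10.5.3 could produce either result and cite the protocol for it. A reader of the report would not know from the protocol which one was meant as primary.

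**Working it through.** **Which subjects differ.** Applying protocol 10.4 to subjects with measurable disease at baseline:

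| Subject | Response Evaluable | Measurable disease at baseline |
|---|---|---|
| Has a post-baseline assessment | included | included |
| No assessment, withdrawn for PD or death | included, non-responder | included, non-responder |
| No assessment, any other reason | excluded | included, non-responder |

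Only the third row separates the two denominators.

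**How large that row can be.** Stopping treatment does not end imaging. Both schedules of assessments require a scan at end of treatment unless one was done within 4 weeks. Protocol 6.4 continues scans until PD even if study drug has stopped, unless consent is withdrawn. Protocol 4.1.4 and 6.5 require imaging every 3 months for those who stop without radiographic progression, until progression or new therapy. A subject who stops for toxicity but stays in follow-up would normally be scanned and be in both sets. The third row is mainly consent withdrawal, loss to follow-up and missed scans.

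**Arithmetic.** The plan gives no ORR hypothesis, assumed response rate or dropout rate, so there is no planned figure to reproduce. Inputs:

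- N = 50, the approximate Part 2 size (protocol 10.2, SAP 4).
- x = responders, assumed 10, with 5 as a second case.
- k = third-row subjects, assumed 0 to 10.

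Measurable disease at baseline: ORR = x/N. Response Evaluable: ORR = x/(N − k). Difference = xk / [N(N − k)], which is never negative. With n the denominator used, the exact 95% limits are the 0.025 quantile of Beta(x, n − x + 1) and the 0.975 quantile of Beta(x + 1, n − x).

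| k | 10 responders: ORR (95% CI) | 5 responders: ORR (95% CI) |
|---|---|---|
| 0 (same as measurable at baseline) | 10/50 = 20.0% (10.0–33.7) | 5/50 = 10.0% (3.3–21.8) |
| 2 | 10/48 = 20.8% (10.5–35.0) | 5/48 = 10.4% (3.5–22.7) |
| 5 | 10/45 = 22.2% (11.2–37.1) | 5/45 = 11.1% (3.7–24.1) |
| 10 | 10/40 = 25.0% (12.7–41.2) | 5/40 = 12.5% (4.2–26.8) |

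With 10 responders and k = 2, the difference is 10 × 2 / (50 × 48) = 0.8 points. With k = 10 it is 10 × 10 / (50 × 40) = 5.0 points.

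**Keeping a neighbouring issue apart.** SAP 7 defines Response Evaluable without the PD/death clause, asking that subjects meet all eligibility criteria, have measurable disease "and also have at least one post-baseline assessment of tumor response". Suppose 5 of 50 are unscanned, 3 because of PD or death and 2 for other reasons, with 10 responders. The protocol definition gives 10/48 = 20.8% and the SAP definition 10/45 = 22.2%, against 10/50 = 20.0%. The conflict inside 10.5.3 is the step from 50 to 48. The step from 48 to 45 comes from the SAP definition, and correcting that definition would leave the 10.5.3 conflict in place.

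**The case against.** The best defence is that the sponsor's intention is clear. The synopsis, the opening sentences of the ORR and BOR paragraphs in 10.5.3, and SAP 9.2 all name Response Evaluable. The second sentence could then be shorthand for a denominator within that set. This is plausible as to intention but weak as a reading of the text. Everyone in Response Evaluable already has measurable disease, so the phrase would add nothing, and the CBR paragraph names the Response Evaluable total when that is what it means.

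Four stronger readings are tempting, and the documents do not support them:

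- **All early leavers are dropped.** Protocol 10.4 keeps those withdrawn for PD or death before the first assessment, so they are non-responders under both denominators.
- **Everyone who stops early for toxicity is lost.** The end-of-treatment and follow-up imaging rules keep many of them evaluable.
- **The sponsor is free to choose after seeing the data.** SAP 9.2 names Response Evaluable and also plans an all-treated ORR. Because measurable disease is an entry criterion, that all-treated set is close to the second denominator, so both results are already planned. What is missing is a label saying which is primary.
- **SAP 14 conceals a change on this point.** SAP 9.2 follows one of the protocol's own two sentences, so its choice of population is not an undeclared departure.

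It also stands that protocol 10.1 makes all analyses descriptive and that no ORR threshold is stated, so no formal decision turns on the gap.

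**Conclusion.** The contradiction is real and concerns the primary efficacy measure, but its reach is narrow and its effect probably modest. For an assumed 10 responders in 50, the gap runs from 0 to 5.0 points as the number of affected subjects runs from 0 to 10. For 5 responders it runs from 0 to 2.5 points. The upper end needs one subject in five to go unscanned for reasons other than PD or death, for which the documents give no basis. Even the 5.0-point gap is small beside the 23.7-point width of the exact interval for 10/50 (33.7 − 10.0). The direction is certain: Response Evaluable gives an ORR at least as high as the other base. The responder and leaver counts are assumptions, and only the approximate size of 50 comes from the plan. The point is worth correcting because a single-arm primary estimate needs one stated denominator and the correction is nearly free.

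**What to change.** Name one primary denominator for ORR and BOR, in the same words, in protocol 10.5.3, the synopsis and SAP 9.2. The preferred choice is all treated subjects with measurable disease at baseline, with subjects who have no post-baseline assessment counted as non-responders. The word treated must be written in, because the present second sentence of 10.5.3 does not contain it. Label the Response Evaluable analysis as the sensitivity analysis, and record the choice in SAP 14. The synopsis must change too, or it will contradict the corrected section.

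If the sponsor prefers Response Evaluable as primary, removing the second base from the ORR and BOR paragraphs and labelling the all-treated summary as sensitivity would also end the contradiction, but it would keep the upward pull on ORR.

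The cost is wording. SAP 9.2 already plans a Response Evaluable and an all-treated summary, so little or no extra programming is needed. The one disadvantage of the preferred choice is a slightly lower headline ORR if some subjects leave unscanned.
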